## Clarifications to Final SAP reflecting Primary Paper in the New England Journal of Medicine 05-15-2021:

- 1. Throughout the protocol and SAP, we refer to the ABC-SW, which is a modified subscale of the ABC-Lethargy, Social Withdrawal Subscale that eliminated questions 3, 32, and 53, which refer to lack of movement, in order to increase specificity for social reciprocity behaviors. In writing the primary paper, we wanted to eliminate any possible confusion with the original published ABC-Lethargy, Social Withdrawal subscale and referred to the modified scale as the ABC-modified Social Withdrawal subscale or ABC-mSW. We have changed our clinicaltrials.gov primary results to use the new nomenclature of ABC-mSW.
- 2. Reviewers pointed out that it was not entirely clear what our three secondary outcomes were. Therefore, we want to be clear that they are:
  - a. the Sociability Factor (abbreviated SF) which combines the ABC-mSW and the PDD-BI screening version in order to assess both areas of social reciprocity challenges and social skills (there was an error in the original version of the final SAP in which the sociability factor was inadvertently omitted from section 4.1.2, which has been corrected)
  - b.the Social Responsiveness Scale, 2nd Edition Social Motivation Subscale (abbreviated SRS-2-SM); c. the Stanford Binet, 5th edition Abbreviated Intelligence Quotient (abbreviated ABIQ).
- 3. Reviewers requested that we clarify what our sensitivity analyses were. They follow
  - a. Analysis using the original ABC-Lethargy, Social Withdrawal Subscale
  - b. Analysis integrating baseline (or screen if no baseline was available) plasma oxytocin level, baseline oxytocin level x treatment, and baseline oxytocin x treatment x time into the MMRM model
  - c. Analysis separately of the ABC-mSW outcome in the minimally verbal and fluently verbal subgroups.
  - d. Analysis of the ABC-mSW outcome in the per proctocol population
- 4. In the primary paper we also clarify that the full analysis set is essentially a modified intent treat sample, and that age group was dropped from the final analysis model because it was not significant.

Initial Statistical Analysis Plan for SOARS-B

Version 1.0

March 21, 2013

Study of Oxytocin in ASD to Improve Reciprocal Social Behaviors (SOARS-B)

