#### 4.2 General Modelling Considerations for Efficacy Analyses

Unless otherwise specified, the primary model is mixed model with repeated measures (MMRM), with change from baseline to each post-baseline timepoint for a response variable, functioning (low versus high) as the stratification variable, center as a blocking factor, treatment (oxytocin versus placebo), week as a continuous variable, treatment and week interaction, and baseline value as a covariate, with random coefficients for the intercept and week, with an unstructured structure among the random coefficients. We will investigate the interaction of treatment, week, and functioning and adopt the most parsimonious model as the final model. Distributional assumptions will be examined using residuals. These mixed models could fail to converge or encounter difficulties based on their use of asymptotics. If they do, we will attempt to

simplify the models in order to eliminate the problems, and if necessary, move to analyses that assume compound symmetry, but use a Huynh-Feldt correction if compound symmetry fails.

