### 4.4 Primary Efficacy Analysis

The primary efficacy response variable will be tested at the level of  $\alpha$  = 0.05. Longitudinal models as described in General Modeling Considerations will be fit with dependent variable of change from baseline to each post-baseline timepoint (weeks) up to week 24. The primary hypothesis test of interest will be a test of treatment effect at week 24.

As a sensitivity analysis, the primary efficacy analysis will also be conducted in the per-protocol population.

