## **Suggested Titration to the Target Dose**

Blinded Phase: In the double-blind phase, titration to the target dose is expected to take 8 weeks and follow the suggested table below unless there are issues with tolerance or compliance. Dosing will begin at 8/0 IU in the AM at baseline. Typically, the dose will increase to 8/0 IU twice daily (BID) (16/0 IU TDD) at week 2. Dose will then be increased by 8/0 IU twice daily (BID) at weeks 4 and 8 with TDDs of 32/0 IU and 48/0 IU respectively. During the initial titration period (baseline to week 8), dosing increases should never occur before the time point specified in the schedule. Specifically one could not go to a TDD of 16/0 IU prior to week 2, or 32/0 IU prior to week 4 or 48/0 IU prior to week 8.

Week 0	Week 2	Week 4	Week 8
8 IU qD	8 IU BID	16 IU BID	24 IU BID
(8 IU TDD)	(16 IU TDD)	(32 IU TDD)	(48 IU TDD)

**Open Label Phase:** In the open-label phase, from week 24 to week 28, the dose will be 24IU in AM for a TDD of 24 IU. From week 28-36 the dose will be 48 IU TDD (ie. 24 IU BID). At week 36 the dose can be increased to 72 IU TDD (ie. 48 IU in the morning and 24 IU in the afternoon).

Week 24	Week 28
24 IU qAM	24 IU BID
(24 IU TDD)	(48 IU TDD)

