## **Dosing Increases Above Target Dose:**

In the blinded phase after the target dose has been maintained for at least 7 weeks the dose may be increased by 16/0 IU TDD only at each of the subsequent visits. Thus, at week 16, the maximal possible dose will be 64/0 IU TDD. However, at week 20 the dose could be increased to either 64/0 IU TDD if there had been no prior increase at week 16 or, could be increased to 80/0 IU TDD if the dose had been increased at week 16.

In the open-label phase after the target dose has been maintained for  $\sim$  7-8 weeks then the dose can be increased (at week 36) to 72 IU TDD.

**Applies to both phases:** Increases past the target dose are NOT required and may ONLY be made if the following conditions are met

- No evidence of clinically significant adverse events
- Parents agree
- Clinician agrees

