# 10.1 Statistical Analysis (Please also see SAP)

General Modeling: Unless otherwise specified, we will fit a mixed longitudinal model with change from baseline to each post-baseline month (4 weeks) for a response variable, functioning (low versus high) as the stratification variable, center as a blocking factor, treatment (oxytocin versus placebo) as the between-subjects factor, week as a within-subjects factor, their interaction, and baseline as a covariate. The primary model used will be a mixed model with repeated measures (MMRM), treating week categorically and using an autoregressive (with a lag of 1) covariance structure. As a secondary sensitivity analysis, we will fit a random coefficients model treating week continuously with random coefficients for the intercept, slope, and slope squared, with an unstructured structure among the random coefficients. The primary hypothesis test of interest will be a test of treatment effect at week 24. Distributional assumptions will be examined using residuals. These mixed models could fail to converge or encounter difficulties based on their use of asymptotics. If they do, we will attempt to simplify the models in order to eliminate the problems, and if necessary, move to analyses that assume compound symmetry, but use a Huynh-Feldt correction if compound symmetry fails.

Missing Data: The mixed models used to evaluate the continuous response variables are able to handle moderate amounts of missing data provided they are missing at random. We will examine the missing at random assumption by assessing baseline differences between dropouts and completers, as well as differences in response variables up to the point of premature withdrawal. If the missing at random assumption does not appear to be tenable, we will report the mixed models results but spend additional effort characterizing treatment effect at time of premature withdrawal or the effect of not including participants with significant missing data in supplementary analyses.

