# **Procedural Changes:**

- Revised oxytocin dosing schedule to allow more flexibility during double-blind treatment
- Developed specific criteria for increasing oxytocin above target dose
- Developed detailed procedures for increasing or reducing oxytocin dose outside of recommended titration schedule.
- Specified use of a centrally administered randomization only included age group and verbal status as strata and did not include site to minimize uneven cells across full study.
- Made DSM-5 criteria primary inclusion criteria to informed by ADI or ADOS and Steering committee discussion if DSM-5 criteria were positive but ADI/ADOS were not
- Changes to the statistical analysis plan were made both in the protocol and noting should refer to SAP for final plan
- Changed randomization target from 300 to 290 because attrition was lower than expected and the grant funding period was about to expire

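### SAP 4.2 replaces the protocol's categorical-week primary model with a straight line over weeks 4-24, and no planned analysis checks whether the week-24 effect it tests depends on that line.

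*Combined protocol and SAP*

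**What the plan says.** Protocol v6.0, 10.1: "The primary model used will be a mixed model with repeated measures (MMRM), treating week categorically", with an AR(1) covariance. It continues: "As a secondary sensitivity analysis, we will fit a random coefficients model treating week continuously", and that second model has random coefficients for intercept, slope and slope squared. Functioning, center and baseline are in the model.

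SAP v2.0, 4.2 specifies "week as a continuous variable, treatment and week interaction, and baseline value as a covariate, with random coefficients for the intercept and week". It calls this an MMRM, although it is a random-coefficients model linear in week. The categorical-week model and the squared term do not appear.

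SAP v2.0, 4.4: "The primary hypothesis test of interest will be a test of treatment effect at week 24".

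On precedence, the Procedural Changes list in the high-level summary of protocol changes describes the protocol as "noting should refer to SAP for final plan", and the heading of protocol 10.1 also points to the SAP. The SAP model therefore governs.

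On checks, item 3 of the Clarifications to the Final SAP begins "Reviewers requested that we clarify what our sensitivity analyses were". It lists the original subscale, baseline plasma oxytocin, verbal subgroups and the per-protocol population. SAP 4.3 adds a missed-visit pattern-mixture model, and 4.5-4.6 add functioning, age and oxytocin interactions. None of these changes how week enters the model.

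**The concern.** With categorical week and complete data, the week-24 contrast is the arm difference observed at week 24. With a linear treatment-by-week term it is the height at week 24 of a line fitted through six visits. The two agree in general only if the arm difference is linear or constant over weeks 4-24.

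The documents give no trajectory and no reason to expect a line. Dosing is stepped: "In the double-blind phase, titration to the target dose is expected to take 8 weeks", and later "after the target dose has been maintained for at least 7 weeks the dose may be increased by 16/0 IU TDD", which makes weeks 16 and 20 the first points for optional increases. A plateau after titration, or a response that starts late, is as plausible as a line.

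At stake are the size of the reported week-24 effect and the power of the separate-stratum analyses, which are the basis of the sample size (SAP section 6).

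**Working it through.** **Inputs.** ABC-SW visits at weeks 4, 8, 12, 16, 20 and 24 (SAP 2.1.3). SD 9, difference 5, two-sided alpha 0.05, 71 per arm per stratum, final N 290, hence 145 per arm (SAP 2.2 and 6). Effect shapes and within-subject correlations are my assumptions, because the documents give none.

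**The plan's own figure.** n per arm = 2 × 81 × (1.96 + 1.2816)² / 25 = 68.1, so 69 (70 with the t distribution), against 71 stated. Power at 71 per arm: SE = 9√(2/71) = 1.511; P(Z > 1.96 − 5/1.511) = 0.912. The stated figure reproduces to within two patients.

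**Weights.** Mean visit week is 14 and Sxx is 280. The weight of visit t in the fitted week-24 value is 1/6 + 10(t − 14)/280:

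| Week | 4 | 8 | 12 | 16 | 20 | 24 |
|---|---|---|---|---|---|---|
| Weight | −0.190 | −0.048 | 0.095 | 0.238 | 0.381 | 0.524 |

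They sum to 1, and weeks 4-20 contribute 0.476 net. With complete data, generalized least squares gives the same weights under any random intercept-and-slope covariance.

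**Fitted week-24 difference for assumed shapes with a true value of 5.**

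| Arm difference at weeks 4 to 24 | Fitted | Bias |
|---|---|---|
| linear or constant | 5.00 | 0 |
| 2.5, 5, 5, 5, 5, 5 | 5.48 | +10% |
| 1.67, 3.33, 5, 5, 5, 5 | 5.71 | +14% |
| 0, 2.5, 5, 5, 5, 5 | 6.07 | +21% |
| 0, 0, 0, 1.67, 3.33, 5 | 4.29 | −14% |
| 0, 0, 0, 0, 2.5, 5 | 3.57 | −29% |

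For example, the last row is 0.381 × 2.5 + 0.524 × 5 = 3.57. A fade to a true zero (2.5, 5, 5, 3.33, 1.67, 0 or 2.5, 5, 5, 5, 2.5, 0) would give 1.2 or 1.9, but nothing in the documents points to a fade.

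**Standard error.** Under compound symmetry, the ratio of linear to categorical SE is √(ρ + (1 − ρ) × 0.5238): 0.873 at ρ = 0.5, 0.900 at 0.6, 0.951 at 0.8. If the true correlation is AR(1) with 0.85, the ratio is 1.023. The range used below is 0.873 to 1.023.

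**Power per stratum (71 per arm).** Linear-model SE = 1.511 × 0.873 to 1.511 × 1.023, that is 1.319 to 1.545. Power = P(Z > 1.96 − estimate/SE).

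| Shape | Linear week | Categorical week |
|---|---|---|
| linear | 90-97% | 91% |
| plateau (5.48 to 6.07) | 94-99.6% | 91% |
| gradual late onset (4.29) | 79-90% | 91% |
| sharp late onset (3.57) | 64-77% | 91% |

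**Whole sample (145 per arm).** Categorical SE = 9√(2/145) = 1.057, power 99.7%. Sharp late onset under the linear model keeps 91-97%.

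**The case against.** The strongest reply is that this is a sequenced update, not a live conflict. The SAP is later than the protocol and the protocol defers to it. A continuous-time random-coefficients model was one of two candidates from the start, and the sample code for it in the 2013 SAP was already a straight line. That is fair on precedence. It does not supply a reason for linearity, and the other candidate, which would have served as the check, is gone from the governing plan. Protocol 10.1 still lists both alternative models, but a reader sent to the SAP for the final plan would not expect them to be run.

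Second, the extreme shapes may be unrepresentative. If the effect were proportional to the daily dose in force before each visit, the maximum permitted path (16, 32, 48, 48, 64, 80 IU) scaled to 5 at week 24 gives 4.86 (−3%), and the path that stays at target gives 5.71 (+14%). This range is narrower and it stands as a reasonable central range. It still includes a 14% overstatement that nothing planned would reveal.

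Third, the straight line can be more precise, whole-sample power is barely at risk, and the stratum analyses are labelled secondary in SAP 4.5. All true. But the SAP does not argue efficiency, and part of the power gain under a plateau comes from upward bias.

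Fourth, residuals will be examined and protocol section 10 calls for graphical exploration. The residual check in 4.2 is for distributional assumptions, and neither step commits to an alternative week-24 estimate.

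Fifth, a primary paper exists, so changing the primary model now would itself be post hoc. That favours the sensitivity-analysis route where results are already known.

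One limit: the SAP change summary (item 19) mentions added SAS detail, but the text available to me shows no code for the week-24 contrast. The point rests on the wording of 4.2.

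**Conclusion.** The concern holds and should be fixed. The two documents name different primary models. The governing one estimates a week-24 effect through a linearity assumption that the documents neither support nor test.

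The weights depend only on the visit schedule and complete data, so the 48% figure is firm. The biases (+10% to +21% for plateaus, −14% and −29% for late onset) and the powers depend on assumed shapes and correlations. They show what could happen and do not predict it.

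The limits matter. There is no bias under a linear or constant difference, size is kept when the arms differ at no visit, some non-linear shapes give the right value by chance, and whole-sample power stays at about 91% or more even under the sharp late-onset shape. The material exposure is the size of the week-24 estimate and the stratum analyses.

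**What to change.** Reconcile SAP 4.2 with protocol 10.1:

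- **Primary:** MMRM on change in ABC-SW at weeks 4, 8, 12, 16, 20 and 24, with categorical week, treatment, treatment-by-week, functioning, center and baseline. Use AR(1) as in the protocol, or one other covariance structure named in advance. State the test as an explicit treatment contrast at week 24.
- **Sensitivity:** the continuous-week random-coefficients model.
- **Acceptable alternative:** keep the straight line as primary, give the reason, and name the categorical-week model as the sensitivity analysis.
- **Tidy-up:** SRS-2 Social Motivation has only two post-baseline ratings (weeks 12 and 24), so random intercept, random slope and residual cannot be separated. Use categorical week with an unstructured 2×2 covariance. The SRS-2 contrast itself is not affected.
- **Label:** reserve the term MMRM for the categorical-week model.

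The cost is SAP wording and one model call on collected data. Moving from linear to categorical week changes the week-24 standard error by about −2% (AR(1) 0.85) to +15% (compound symmetry 0.5), with +11% and +5% at compound symmetry 0.6 and 0.8.

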#### 2.1.3. Per-Protocol Population

The per-protocol (PP) population is defined as a subset of FAS who complete the full 24 weeks of double blind treatment with study drug (including those who stayed on the study drug for at least 22 weeks with 80% treatment compliance) and all assessments of the ABC-SW at baseline, Weeks 4, 8, 12, 16, 20 and 24. The per-protocol population will be used only for supportive analyses of the primary efficacy endpoint.

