#### 4.3 Missing Data Considerations for Efficacy Analyses

If there is <5% of subjects with covariate data points missing, then no additional sensitivity analyses will be performed. If there are >=5% of subjects with missing covariate data, we will perform multiple imputation (MI). We will use the full conditional specification method (FCS) to impute missing data. If data have a monotone missing pattern, we will use linear regression to impute continuous variables, logistic regression to impute binary/ordinal variables, and the discriminant function to impute nominal variables. We will check normality of continuous variables. If very asymmetric, variables will be transformed. We will create 20 imputed datasets including all variables intended to be used in subsequent statistical analysis as a minimum. We will analyze the complete datasets using standard statistical analyses. Finally, the results from each model will be combined to produce inferential results.

If there is <5% of subjects with efficacy outcome data points missing, this will be considered a negligible amount and no additional sensitivity analyses will be performed. If there are >=5% of subjects with missing outcome data, the Mixed-Effect Model Repeated Measure (MMRM) approach is able to handle moderate amounts of missing data provided they are missing at random. However, it is difficult to rule out the possibility that at least some of the missing data are missing not at random (MNAR). We will apply a pattern-mixture approach to investigate the MNAR pattern. Specifically, we will define the missed visit indicator (1 if missing and 0 if observed). We fit a pattern-mixture MMRM model with this defined missed visit indicator. The coefficient of the missed visit indicator (e.g., gamma) is estimated and tested for statistical significance. If this coefficient is not statistically different from zero, missing at random assumption is valid. Otherwise, the missing is not at random. If the latter, we conduct an extensive sensitivity analysis by pre-specifying the value of gamma, which plays the role of sensitivity parameter to the MAR assumption. We define a grid in a plausible range of sensitivity parameter. For each pre-specified value, we investigate the treatment effect. When the pre-specified value is zero, the analysis assumes MAR.

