#### 6. SAMPLE SIZE AND STATISTICAL POWER CONSIDERATION

We will use a mixed longitudinal model for our primary analyses (see Efficacy Analyses section). Since some aspects of the model such as covariance structure are unknown, we performed power and sample size calculations using a more conservative, simplified model corresponding to a two-group t-test on change scores. SOARS-B is powered to allow independent evaluation of oxytocin efficacy in low and high-functioning youth.

Standard deviations of change scores for the ABC-SW range from  $^{\sim}5$  to 9 in several large ASD intervention trials (Shea 2004; McCracken 2002; Owen 2009; Marcus 2009, [name] 2009; Aman 2009). We consider a between groups difference of 5-7 points in ABC-SW change scores to be clinically meaningful. In our power calculations, we use conservative estimates of 9 points for the SD of ABC-SW change and 5 points for between group differences in ABC-SW changes (differential improvement on  $^{\sim}1/3$  of items). To achieve 90% power with an alpha of 0.05 on the ABC-SW, we will require 71 participants in each treatment group within the two strata. Thus, our total required sample to evaluate the ABC-SW separately in low and high-functioning strata is 284. A sample size of 300 will allow for 5% attrition between randomization and the first post-randomization visit. On 3/28/2016, the study team reduced the attrition rate to 1% based on attrition observed in the study, which gives a final sample size of 290. The primary objective considers all participants, resulting in much greater power than for analyses in separate strata.

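### SAP 4.2 gives baseline one coefficient for all weeks; if its effect drifts, leaving out baseline-by-week costs a little precision and can slightly bias the week-24 contrast under arm-dependent dropout

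*Combined protocol and SAP*

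**What the plan says.** SAP v2.0, section 4.2, models change from baseline at each post-baseline visit. The fixed effects are functioning, center, treatment, "week as a continuous variable, treatment and week interaction, and baseline value as a covariate". The random part is specified "with random coefficients for the intercept and week, with an unstructured structure among the random coefficients". Baseline enters as a main effect only. The one further interaction that section 4.2 considers concerns functioning, not the baseline score: "We will investigate the interaction of treatment, week, and functioning and adopt the most parsimonious model as the final model".

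Section 4.4 fixes the target: "The primary hypothesis test of interest will be a test of treatment effect at week 24". The visits that feed the model can be read from the per-protocol definition in section 2.1.3, which requires "all assessments of the ABC-SW at baseline, Weeks 4, 8, 12, 16, 20 and 24". Section 4.6 adds interactions with age and baseline oxytocin, and none with baseline score. Protocol v6.0, section 10.1, also enters baseline simply as a covariate.

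On missing outcomes, section 4.3 says that the mixed-model "approach is able to handle moderate amounts of missing data provided they are missing at random".

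**The concern.** With change as the outcome and equal SDs at baseline and follow-up, the regression of change on baseline at week t is rho(t) - 1, where rho(t) is the correlation of the week-t score with baseline. If that correlation falls as time passes, the coefficient becomes more negative. The planned model cannot follow this. It fits one compromise value and leaves the rest in the random slope, and the week-24 contrast depends on the slope.

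Two things follow if there is drift. Unexplained slope variation widens the standard error. And the protection given by missing at random holds only if the mean model for baseline is right. Suppose severe children leave one arm and mild children leave the other. The children who remain then differ between arms in expected slope, and the model credits part of that difference to treatment.

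The ingredients are plausible. Protocol v6.0, section 4.3, sets no minimum ABC-SW score. SAP 3.1 lists adverse effects and lack of efficacy among the reasons for early termination, and these could relate to severity differently by arm.

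**Working it through.** **The plan's own figure.** SAP section 6 uses a difference of 5, an SD of 9 and the target "To achieve 90% power with an alpha of 0.05 on the ABC-SW" (two-sided, section 2.2). Per arm and stratum, n = 2 x (1.960 + 1.282)^2 x 9^2 / 5^2 = 2 x 10.51 x 3.24 = 68.1, so 69. The exact t calculation gives 70, and power at the stated 71 is 0.91. The figure reproduces.

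**Model.** Leaving aside functioning and center, the planned mean is mu + g*trt + d*t + h*trt*t + b*B, with contrast g + 24h. If the true coefficient of B is b(t), the unmodelled part at week 24 is [b(24) - b]*B. Roughly, and before the random slope recovers some of it, bias = [b(24) - b] x (difference between arms in mean baseline of the children still observed). Both factors must be non-zero.

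**Inputs.** From the documents: 290 children, 1:1 allocation (145 per arm), six visits, and an SD of change of 9. Assumed, because the documents do not give them: baseline SD 9, residual SD 4, random-intercept SD 5, intercept-slope correlation -0.3, 0 or 0.3, true effect 0, and 5-20% dropout by week 24 that depends only on baseline (log-odds 1 per SD). Three baseline effects were tried from week 4 to week 24: constant at -0.40, -0.30 to -0.45 (mild drift), and -0.20 to -0.50 (strong drift).

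**Precision, by hand.** The planned model settled on b of about -0.32 to -0.34 under mild drift, a gap of 0.11-0.13 at week 24, and on about -0.26 to -0.28 under strong drift, a gap of 0.22-0.24.
- Mild: (0.11 x 9)^2 = 0.98 to (0.13 x 9)^2 = 1.37, against 81 - (0.45 x 9)^2 = 64.6, or 1.5-2.1%.
- Strong: (0.22 x 9)^2 = 3.9 to (0.24 x 9)^2 = 4.7, against 81 - (0.50 x 9)^2 = 60.75, or 6.5-7.7%.

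Simulation without dropout gave about 2% and 7-8%. With a constant effect the variance ratio was 1.00.

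**Bias.** Large-sample bias in ABC-SW points, with dropout in opposite directions by arm and intercept-slope correlation 0:

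| Baseline effect, week 4 to 24 | 5% dropout | 10% | 20% |
|---|---|---|---|
| Constant -0.40 | none | none | none |
| -0.30 to -0.45 | 0.11 | 0.19 | 0.30 |
| -0.20 to -0.50 | 0.19 | 0.34 | 0.58 |

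Over the three correlations the drifting cases ranged from 0.08 to 0.61. With baseline-by-week added, estimates were about 0.00-0.04, within simulation error (SE about 0.035). With the same dependence in both arms, the two models differed by no more than 0.02.

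**Second set of assumptions.** Baseline SD 8, week-24 change SD 7.3-8.0, about 13% dropout by week 24, and baseline coefficient -(0.15 + c x week). For c = 0.005, 0.010 and 0.015 the coefficient moves from -0.17 to -0.27, -0.19 to -0.39, and -0.21 to -0.51.
- Variance penalty: about 1%, 3% and 7%.
- Bias, opposite directions: 0.13, 0.24 and 0.34.
- Bias, one arm only: 0.08, 0.13 and 0.17.
- Bias with the term added: 0.02 or less.

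**Scale.** 0.1/5 = 2% and 0.6/5 = 12% of the design difference. The standard error of the contrast is about 0.9, so the bias is roughly 0.1 to 0.65 standard errors. At 145 per arm, with drift and opposite-direction dropout, rejection under the null was 0.05-0.07 without the term and 0.04-0.05 with it. With 500 replicates the simulation SE is sqrt(0.05 x 0.95 / 500) = 0.010, so this does not establish a material rise in type I error.

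**The case against.** The strongest objection is that neither trigger is in the documents. Nothing shows that the baseline effect changes between weeks 4 and 24, and nothing shows dropout that depends on severity differently by arm. Treatment is double-blind, and the pooled pilot data in protocol v6.0, section 1.3, are said to show no excess of adverse events on oxytocin. This stands. A reader might infer that the primary model is misspecified and the week-24 result biased. The documents support only the conditional statement.

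A reader might also take the 1% attrition figure in SAP section 6 as proof that dropout is negligible. It is not: it replaces a 5% rate defined only up to the first post-randomization visit. Dropout to week 24 is not given, and section 4.3 itself provides for 5% or more missing outcomes.

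There are partial safeguards. Protocol 10.1 compares dropouts with completers at baseline, protocol 6.5 sends the week-24 questionnaires to children who stop early, and residuals will be examined. These may reveal the problem but do not correct it. The pattern-mixture step in SAP 4.3 tests a missed-visit indicator, which is aimed at data not missing at random and does not repair the baseline-by-time mean.

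Finally, a linear interaction succeeds by construction when the simulated drift is linear. That is fair, but the term also left essentially no bias when the baseline effect was made to level off.

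**Conclusion.** The point holds as a conditional, minor one. SAP 4.2 fixes one baseline coefficient for all weeks. If the true effect drifts, the omission costs about 1-8% in variance of the week-24 contrast. If, in addition, dropout depends on baseline differently by arm, it can move that contrast by roughly 0.1-0.6 ABC-SW points at an assumed 5-20% dropout. The sign depends on which arm loses the more severe children. If the effect does not drift, both costs vanish; if dropout depends on baseline alike in both arms, the bias essentially vanishes.

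The sizes rest on assumed values for baseline SD, drift and dropout. Even the largest is about one eighth of the 5-point difference. This is a free improvement to the primary analysis and not a defect that threatens its conclusion.

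**What to change.** In SAP 4.2, add baseline-by-week to the pre-specified fixed effects, for ABC-SW and for every other outcome analysed with this longitudinal model. Outcomes measured only at baseline and week 24, which section 4.7 sends to a two-sample t-test, are unaffected. Keep the treatment contrast at week 24 as in section 4.4. State that the term stays in the model whatever its p-value, so that the search for the most parsimonious model in section 4.2 cannot remove it.

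The cost is one degree of freedom with week continuous, and no new data. When the term is not needed, the variance of the contrast rises by less than 1%.
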